9.4.4 SAFETY ANALYSES

N/A

9.4.5 BASELINE DESCRIPTIVE STATISTICS

We will describe baseline characteristics such as age, sex, race, state anxiety, thyroid cancer fear, and clinical history such as hypothyroidism overall and by treatment arm, consistent with CONSORT checklist criteria.

9.4.6 PLANNED INTERIM ANALYSES

N/A

9.4.7 SUB-GROUP ANALYSES

For the primary endpoint, we will determine whether differences exist in response to the intervention by age, sex, race/ethnicity, and level of education. Prior data suggests disparities may exist in treatment received for actual patients with thyroid cancer and these characteristics. We will also determine if differences exist by clinical characteristics, such as hypothyroidism, thyroid-related symptoms, personal history of cancer, nodule characteristics, time of diagnosis, and medical use tendencies, again based on the published literature in patients with thyroid or other low-risk cancers.

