Intervention: We have created two videos using rigorous methods described by van Vleit et al. for creating internally and externally valid videos that manipulate affective communication.⁵¹ The videos are 5-6 minutes in length and portray a conversation between a patient and surgeon during which the surgeon discusses: the diagnosis, prognosis, available treatment options, benefits and harms of the options, and need for decision making. The surgeon speaks for the majority of the simulated visit and discusses total and hemi-thyroidectomy. The scripts are identical between arms except for the addition of emotionally supportive statements and

gestures in the intervention script. This study design using simulated patient-provider conversations that manipulate affective communication in analogue patients has been employed by others and successfully translated back into clinical practice for the development of effective physician-based interventions.^{42-44,46}

Randomization: Participants will be stratified based on sex. Males are more likely to undergo less extensive treatment.¹² After completion of consent and the pre-intervention survey that includes demographics, Qualtrics will direct participants into two separate survey branches: males and females. Qualtrics will randomize participants 1:1 to a video within each branch. They will then proceed to the post-intervention measures. Study staff will not know participants' arm assignment.

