9.2 SAMPLE SIZE DETERMINATION

We assume based on existing data that the proportion of participants choosing total thyroidectomy will be 0.89 and estimate the sample size needed for 90% power to detect a proportion lower than 89%. With a sample of n=59 in each group, we will be able to detect risk differences of -25% and medium effect sizes of -0.60 with 90% power using a 2-sided test (chi square for binary outcome) with Type I error rate alpha= 0.05. The UW Thyroid Nodule Biopsy clinic performs over 500 biopsies annually, of which approximately 70% are benign. The UW Radiology clinic performs 400 biopsies per year on patients with benign thyroid nodules.

We anticipate missing data will be very low as the study is expected to be completed in one sitting.

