9.4 STATISTICAL ANALYSES

9.4.1 GENERAL APPROACH

For descriptive statistics, categorical and continuous data will be presented as percentages, means with standard deviations, median, and range. For inferential tests, we will use 2-sided tests with Type I error rate alpha=0.05 for statistical significance. Covariates are specified below. Checks for assumptions of normality will be performed. If data are not normal, nonparametric tests will be used.

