9.4.2 ANALYSIS OF THE PRIMARY ENDPOINT(S)

The primary endpoint, treatment choice, is a binary scale. It will be measured once immediately after the intervention.

We will calculate distributional characteristics and perform a two-group intent to treat analysis for this binary endpoint using conditional logistic regression to account for stratification by sex. The Type I error rate alpha= 0.05.

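### Do the treatment-choice subgroup analyses in 9.4.7 need a stated interaction model, effect scale and sparse-cell method?

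*Combined protocol and SAP*

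**What the plan says.** Section 9.4.7 states that, for treatment choice, "we will determine whether differences exist in response to the intervention by age, sex, race/ethnicity, and level of education". It continues "We will also determine if differences exist by clinical characteristics" and gives six examples, which makes ten named factors in an open list. The reason offered is that "Prior data suggests disparities may exist in treatment received for actual patients with thyroid cancer and these characteristics". The section gives no interaction model or test, effect measure, cut-points or rule for sparse cells.

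The only model named for treatment choice is in 9.4.2, "using conditional logistic regression to account for stratification by sex". That section names no effect measure; an odds ratio is implied by the model. The sample size in 9.2 works on the risk-difference scale: "We assume based on existing data that the proportion of participants choosing total thyroidectomy will be 0.89", and "With a sample of n=59 in each group, we will be able to detect risk differences of -25" percentage points with 90% power. The general fallback in 9.4.1, "If data are not normal, nonparametric tests will be used", concerns non-normal data and does not bear on a binary outcome. Section 4.1 explains stratification by sex with the remark "Males are more likely to undergo less extensive treatment".

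Subgroup analyses of the secondary endpoints sit in 9.4.9 under the exploratory heading. Those of the primary endpoint do not carry that label.

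**The concern.** Two features look troublesome together.

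- **Sparse cells.** If 89% of control participants choose total thyroidectomy, the few who choose otherwise are divided over the levels of each modifier. When every participant in one arm-by-subgroup cell makes the same choice, the interaction log odds ratio is infinite and its Wald interval is useless. A substitute method would then be chosen with the data in view.
- **Scale.** The trial is sized on a risk difference and its primary model works on log-odds. When control rates differ between subgroups, as the protocol's remark about sex suggests they may, equal response on one scale is unequal response on the other. Two analysts could then rank the same subgroups in opposite order.

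At stake would be the credibility of statements about who responds to supportive communication. The overall comparison of the two videos is not at stake.

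**Working it through.** **Inputs.** From 9.2: control rate 0.89, difference -0.25 (so 0.64), 59 per arm, two-sided alpha 0.05, 90% power. From 9.4.7: ten named factors. Subgroup shares, the sex ratio and sex-specific rates are not in the documents, so all values used for them are assumptions.

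**The plan's own figure.** With pooled rate (0.89 + 0.64)/2 = 0.765,

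n = [1.96 √(2 × 0.765 × 0.235) + 1.2816 √(0.89 × 0.11 + 0.64 × 0.36)]² / 0.25² = 58.3,

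which rounds up to 59 per arm (power 0.903). The stated size reproduces.

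**Sparse cells.** Expected control participants choosing hemi-thyroidectomy: 59 × 0.11 = 6.5. A control cell of n people contains none with probability 0.89ⁿ: 25% for n = 12 (a 20% subgroup), 12% for n = 18 (30%), 3% for n = 30 (50%).

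Simulating whole two-level factors, with the same rates in each subgroup, gives the chance of no finite interaction estimate:

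| Share in smaller level | 0.89 vs 0.64 | 0.89 in both arms |
|---|---|---|
| 50% | 7% | 14% |
| 40% | 9% | 17% |
| 30% | 15% | 27% |
| 20% | 28% | 47% |
| 10% | 59% | 77% |

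Four-level factors do worse: 59% and 83% with equal levels, 77% and 93% with a 40/30/20/10 split. Age kept continuous does better: about 0% and 5%.

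For at least one failure among ten binary modifiers assigned independently of each other:

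| Shares | 0.89 vs 0.64 | 0.89 in both arms |
|---|---|---|
| All 50% | 33% | 55% |
| Spread over 20-50% | 64% | 86% |
| All 20% | 91% | 99% |

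These are lower than multiplying the single-factor chances would give, because every modifier divides the same few hemi-thyroidectomy choosers and failures cluster. In the spread case the mean number affected is 1.4 and 2.5 of ten.

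**Does an infinite estimate stop the analysis?** Section 9.4.7 asks whether differences exist, which a test can answer. Take a 20% subgroup with 12 of 12 control and 6 of 12 intervention participants choosing total thyroidectomy, and 41 of 47 and 31 of 47 in the remainder. The interaction log odds ratio is infinite. The likelihood-ratio test against the model without interaction gives chi-square 3.88 on 1 degree of freedom, p = 0.049. Only the Wald estimate and its interval fail.

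**Scale.** The planned odds ratio is (0.64/0.36)/(0.89/0.11) = 0.22. Assume control rates of 0.92 in women and 0.80 in men with 25% men: 0.75 × 0.92 + 0.25 × 0.80 = 0.89. An odds ratio of 0.22 in both sexes then means -20 points in women and -33 in men. True differences of -22 and -28 points give odds ratios (0.70/0.30)/(0.92/0.08) = 0.20 and (0.52/0.48)/(0.80/0.20) = 0.27, so the order does reverse.

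In 200,000 simulated trials per case (15 men and 44 women per arm, 0.5 added to each cell for the log-odds), the two interaction estimates had opposite signs in 20-26% of trials with these unequal control rates. With equal control rates and a uniform -25 points the figure was already 12-13%. Among opposite-sign trials with unequal rates, the median absolute z for the risk-difference interaction was 0.33-0.45. Both 95% intervals excluded zero in opposite directions in no trial. The signs differed and at least one interval excluded zero in at most 0.15% of trials.

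**The case for a change.** The strongest case for a change is that the plan leaves every choice open at once. The factor list is open-ended, race/ethnicity and education naturally have several levels, and with ten factors some non-finite estimate is more likely than not unless the splits are fairly even. Choosing a penalised, exact or risk-difference method after seeing which cells are empty gives freedom that a sentence written in advance would remove. The absence of an exploratory label, when 9.4.9 applies one to the secondary endpoints, could be read as a stronger claim for these analyses.

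Part of this stands. The detail is missing, and the frequency of empty cells is real for small or multi-level factors. Three things limit it.

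- The document does not say that the 9.4.2 model is used for subgroups, so there is no stated rule that produces a wrong result.
- Dependence on scale is a property of any binary endpoint with unequal baseline rates. Choosing between odds ratio and risk difference is a trade-off: one agrees with the primary model, the other reads more easily and tolerates sparse cells better.
- Subgroup effects appear in neither the objectives in section 3 nor the hypotheses in 9.1, and 9.2 sizes only the overall comparison. Power to detect -25 points in the larger subgroup against none in the smaller is below 50% on either scale for shares of 20-50%. These analyses are descriptive in substance whatever their heading.

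**Conclusion.** The concern identifies a true gap in detail but not a fault that calls for a change. At the planned rates, a two-level modifier with a 20-50% smaller share has a 7-28% chance of a non-finite interaction estimate, or 14-47% if the videos have no effect. Smaller or multi-level factors fare worse, and continuous age is nearly unaffected. All of this rests on assumed shares and on the logistic model being carried over from 9.4.2.

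When the failure occurs it shows plainly in the output, and a competent analyst would use a likelihood-ratio test, a penalised (Firth) fit or risk differences with a suitable interval. The reversal between scales is arithmetically possible, but in the simulated cases it arose almost entirely when the estimated interactions were near zero, and it never produced contradictory intervals. Writing the model, categories and scale into 9.4.7 would be harmless tidying. It would not alter the primary analysis, the sample size or any conclusion that the trial is designed to support.

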9.4.8 TABULATION OF INDIVIDUAL PARTICIPANT DATA

Individual participant data will not be listed by measure and time point.

9.4.9 EXPLORATORY ANALYSES

We will explore the association of the secondary outcomes of decision confidence, anxiety, and thyroid cancer fear on the primary outcome: treatment choice. We will also perform sub-group analysis for the secondary end points by age, sex, race/ethnicity, level of education, hypothyroidism, thyroid-related symptoms, personal history of cancer, nodule characteristics, time of diagnosis, and medical use tendencies.

10 SUPPORTING DOCUMENTATION AND OPERATIONAL CONSIDERATIONS

10.1 REGULATORY, ETHICAL, AND STUDY OVERSIGHT CONSIDERATIONS

10.1.1 INFORMED CONSENT PROCESS

10.1.1.1 CONSENT/ASSENT AND OTHER INFORMATIONAL DOCUMENTS PROVIDED TO PARTICIPANTS

All potential participants (i.e. adults getting thyroid nodule biopsies) will receive a letter with a URL for uwchoices.org, and an informational brochure about the study. Potential participants who are confirmed to be eligible will be given a link to complete the study on Qualtrics. After passing eligibility screening questions, they will see an information page describing the study intervention, study procedures, and risks. The information page will tell participants to contact the study team with any additional questions about the study.

10.1.1.2 CONSENT PROCEDURES AND DOCUMENTATION

This clinical trial is a hypothetical choice experiment that presents no more than minimal risk of harm to subjects. It involves no procedures for which written consent is normally required outside of the research context. Therefore we will have a waiver of signed consent and present an information page to participants on Qualtrics. Participants will be asked to contact the study team with any questions before proceeding to the study. At the end of the information page on Qualtrics, participants will be told that clicking to the next page indicates their consent to participate in the study.

10.1.2 STUDY DISCONTINUATION AND CLOSURE

This study may be temporarily suspended or prematurely terminated if there is sufficient reasonable cause. Written notification, documenting the reason for study suspension or termination, will be provided by the suspending or terminating party to investigator, funding agency, and regulatory authorities. If the study is prematurely terminated or suspended, the Principal Investigator (PI) will promptly inform the Institutional Review Board (IRB), and sponsor/funding agency and will provide the reason(s) for the termination or suspension.

Circumstances that may warrant termination or suspension include, but are not limited to:

- Determination of unexpected, significant, or unacceptable risk to participants
- Insufficient compliance of study staff to the protocol (i.e., significant protocol violations)

- Data that are not sufficiently complete and/or evaluable

The study may resume once concerns about safety, protocol compliance, and data quality are addressed, and satisfy the funding agency, sponsor, IRB, or other relevant regulatory or oversight bodies (OHRP, DSMB).

10.1.3 CONFIDENTIALITY AND PRIVACY

All research activities will be conducted in as private a setting as possible.

Participant confidentiality and privacy is strictly held in trust by the participating investigators, their staff, and the funding agency. This confidentiality is extended to the data being collected as part of this study. Data that could be used to identify a specific study participant will be held in strict confidence within the research team.

To ensure confidentiality, study data will only be accessed by personnel on the research team. Only the minimum amount of information that is necessary to achieve the aims of the research will be collected. All information obtained and associated data files will be confidential and will be kept in a locked file in a locked office or on a secure, password-protected server within the Department of Surgery network, which is protected by a firewall that ensures the privacy of the network. Any paper records will be kept in a locked cabinet in a locked office that only study staff have access to. Access to the information is limited to the study team, all of whom have completed the requisite human subjects/Health Insurance Portability and Accountability Act (HIPAA) training and have been given valid access to electronic medical records.

Patient information is limited to the minimum necessary to screen for eligibility, recruit patients, and mail participant incentives. The study participant's contact information will be securely stored for internal use during the study. We will also use names, MRNs, and dates/times of appointments. Identifying information will be separated from study data. Once the study is complete, all PHI will be destroyed. At the end of the study, all records will continue to be kept in a secure location for 7 years or longer.

Confidentiality will be protected further by: 1) using a participant log form that contains only the minimum necessary protected health information (PHI) concerning participants and storing this log on a secure password-protected server; 2) coding data collection forms with a consecutive participant number that is not derived from any participant personal identifiers and linking that data collection form to the participant log; 3) storing the participant log and data collection forms separately; and 4) not sharing PHI with anyone outside the research team. It is highly likely that these measures will result in avoidance of breach of confidentiality outside of the research. In addition, the data to be collected are not sensitive to participants.

Survey data will be stored on a secure Department of Surgery server. Data will be shared with Drs. [name] and [name] at the University of Michigan to assist with analysis. The data will not include identifiable information or the keycode. This information will be shared using the secure server file transfer service maintained by the UW Department of Surgery at t.surgery.wisc.edu. This is a secure, password-protected system and files transferred through it are automatically deleted from the service 7 days after upload.

It is NIH policy that the results and accomplishments of the activities that it funds should be made available to the public. The PI will ensure all mechanisms used to share data will include proper plans and safeguards for

the protection of privacy, confidentiality, and security for data dissemination and reuse (e.g., all data will be thoroughly de-identified and will not be traceable to a specific study participant). Plans for archiving and long-term preservation of the data will be implemented, as appropriate.

10.1.4 FUTURE USE OF STORED SPECIMENS AND DATA

Data collected for this study will be analyzed and stored at the University of Wisconsin. After the study is completed, the de-identified, archived data may be transmitted to and stored at a data repository for use by other researchers including those outside of the study. Permission to transmit data to a data repository will be included in the informed consent.

We will obtain IRB approval for any future research projects that might use data from this study.

10.1.6 SAFETY OVERSIGHT

The current study will pose minimal risk to the participants. Participants will be made aware of the risks and benefits which they may incur from participating and will have time to ask questions. Further, they will be told their participation is voluntary and may leave the study at any time at no harm to them.

The PI will be directly responsible for identifying and reporting all adverse events to the IRBs and funding agency as appropriate. Study staff will report any adverse event or unanticipated problem to the PIs immediately. The PIs will report any serious, unexpected, and study-related adverse event or unanticipated problem to the local University of Wisconsin (UW) Minimal Risk IRB according to the institution's requirements. The IRB will review all adverse events during continuing review, which will likely occur annually. Given that our intervention is a hypothetical choice experiment for patients who have benign thyroid nodules, rather than a clinical intervention, we do not anticipate any problems.

We will use the UW's Institute for Clinical and Translational Research's (ICTR) Data Monitoring Committee (DMC). ICTR is UW's NIH Clinical and Translational Science Award and provides extensive research support.

The ICTR DMC will ensure appropriate measures are in place to promote subject safety, research integrity, and compliance with federal regulations and local policies.

The UW ICTR DMC is comprised of experienced members (core plus ad hoc) with expertise required to oversee this study. The DMC members will review protocol-specific reports created by statisticians using data provided by the study team. These standard reports will include an overview of study objectives, a review of actual and projected accrual rates, an evaluation of patient demographics for balance of randomization, and a summary of the number and seriousness of adverse events. Source documents may be reviewed to allow the DMC to independently judge whether the overall integrity and conduct of the protocol remain acceptable based on data provided and reported by the PI. The DMC will make recommendations to the Principal Investigator that could include actions of continuation, modification, suspension, or termination.

In providing oversight for the conduct of this study, the ICTR DMC will meet with the PI prior to data collection, after the first few participants have been enrolled, and at least biannually thereafter to review enrollment and adverse events. Additional meetings will be scheduled as determined by the DMC or as requested by the PI. Because this study is minimal risk, there are no planned interim analyses or predefined stopping points due to futility, efficacy, or harms. We will submit all reportable events to the DMC and the UW Minimal Risk IRB in accordance with their reporting guidelines.

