2.3.3 ASSESSMENT OF POTENTIAL RISKS AND BENEFITS

This study presents minimal risks to participants, as the probability and magnitude of harm or discomfort anticipated in the research are not greater in and of themselves than those ordinarily encountered in daily life. The risks of this study are outweighed by the benefits as the study poses minimal risk to participants. In the future, a better understanding of factors that impact cancer fear may benefit patients. As such, participants benefit by knowing that they are helping future cancer patients.

Participants will be informed that participation is voluntary and they may skip questions they do not want to answer and/or decline to complete the study. They will be reminded to contact their provider if they experience emotional distress.

Multiple steps have been incorporated to reduce the likelihood of a breach in confidentiality. Furthermore, if a breach in confidentiality occurs, it will not negatively impact these participants because the data collected are not sensitive or stigmatizing in any way.

Study investigators and staff will be alert for any potential harms to participants, including breaches of confidentiality. Any breach of confidentiality will be immediately reported to the principal investigator and the UW-Madison Minimal Risk IRB, and the UW-Madison HIPAA Privacy and Security Officers. The risk of breach of confidentiality is low because adequate provisions are in place to ensure that breach of confidentiality will not occur, as described in **section 10.1.3**.

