Potentially eligible patients will arrive to clinic, undergo needle biopsy of their thyroid nodule, and receive a study brochure. Cytology results are automatically released to patients via MyChart and the ordering physician calls the patient within 24-48 hours with their results. Once a benign diagnosis and eligibility is confirmed via chart review, we will approach patients and enroll interested participants within 30 days of their diagnosis. Patients will complete the study in one sitting on a computer or tablet in their own home by accessing a Qualtrics link at a time that is convenient for them. They will confirm their eligibility through screening questions and then proceed to the information page with consent language. If they have questions about the information page, they are directed to contact the study team before indicating consent. Once they indicate consent they will proceed to the pre-intervention survey (administered prior to randomization) which will include demographics (sex assigned at birth, age, race, ethnicity, education, personal cancer history, clinical history regarding their recent biopsy, and baseline measures including the STAI-6 and thyroid cancer fear scale.^{47,48} Participants will then get randomized by Qualtrics to a study arm. After viewing the video, they will complete measures including the STAI-6, an adapted cancer fear scale, manipulation check, physician empathy scale, trust in physician scale, a 5-question information recall questionnaire about the treatment options discussed in the video, and the following questions: (1) “If you were the patient in the video, which treatment option would you choose for yourself?” and (2) “How confident do you feel that you would be choosing the best treatment option for you?” on a 10-point scale [not at all confident to completely confident].⁴⁷⁻⁵⁰ Our primary outcome is treatment choice: total or hemi-thyroidectomy. We chose the STAI-6 because of its predictive validity in assessing changes induced by hypothetical choice experiments in patients with cancer.^{41,45} Our post-intervention measures are further described in **Section 8.1**. Participation is expected to take less than 30 minutes to complete.

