We have designed study procedures including consent, baseline measures, intervention, and outcome measures to all take place in less than 30 minutes on one day, therefore we anticipate attrition will be low. We will be available by phone or email to answer questions that may arise during participation.

Participant Incentive:

All participants will receive a \$40 check, cash, or gift card for completing the study.

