8 STUDY ASSESSMENTS AND PROCEDURES

8.1 ENDPOINT AND OTHER NON-SAFETY ASSESSMENTS

Screening and eligibility assessments: Study staff with UW Health electronic health record (Health Link) access will identify biopsy patients and verify eligibility criteria in Health Link within 21 days of biopsy. If the patient appears to be eligible, a member of the study team will contact the patient via phone and mail (and

MyChart, if available through CHI2) to recruit them for the study. Patients will be provided a link to the study on Qualtrics, where they can answer questions to verify their eligibility criteria and proceed to participation if eligible. Eligibility criteria verified at each screening stage is described in **sections 5.1 and 5.2**. Reasons for screening patients out will be documented at each step of the process. Age and sex of eligible patients will be retained for all eligible patients, including those who decline to participate, to assess any bias between respondents and non-respondents.

Study data: Data will be collected virtually. Mode of data collection will not have adverse effects on our ability to test our study hypotheses. All study measurements will be entered by the participant into Qualtrics.

Baseline demographic and clinical characteristics: We will collect age, sex assigned at birth, clinical history of their thyroid, ethnicity, race, highest educational level attained, anxiety, and level of thyroid cancer fear.

Primary and secondary outcomes:

Type	Name	Timing of Measure	Brief description
Primary	Treatment choice	Post-intervention	We will assess patients' hypothetical treatment choice after the intervention. We will ask: "If you were the patient in the video and had recently been diagnosed with thyroid cancer, which of the two treatment options would you choose, knowing what you know right now?" Answers will include: removal of the entire thyroid, removal of half of the thyroid.
Secondary	Decision confidence	Post-intervention	We will assess patients' confidence in their treatment choice after the intervention. We will ask: "How confident do you feel that you are choosing the best treatment option for you?" Answers will range from 1 (not at all confident) to 10 (completely confident).

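### The DMC and IRB are to receive an adverse-event count, but no described step asks participants about adverse events, so a count of zero could say little about the true rate

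*Combined protocol and SAP*

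**What the plan says.** Section 10.1.6 assigns the duties: "The PI will be directly responsible for identifying and reporting all adverse events to the IRBs and funding agency as appropriate", and "Study staff will report any adverse event or unanticipated problem to the PIs immediately". The DMC's standard reports, built from study-team data, are to contain "a summary of the number and seriousness of adverse events". The DMC meets at least biannually to review enrollment and adverse events, and it may recommend modification, suspension or termination. The schedule of activities has an adverse-event reporting row, marked at the single study session.

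On conduct, section 4.1 says: "Patients will complete the study in one sitting on a computer or tablet in their own home by accessing a Qualtrics link". Section 8.1 adds: "All study measurements will be entered by the participant into Qualtrics". Its table lists treatment choice, confidence, a manipulation check, STAI-6, cancer fear, empathy, trust and recall, with no adverse-event item. Section 8.2 (safety assessments) is marked not applicable. Headings 8.3.1 to 8.3.9 carry no text in the document as supplied.

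On contact, section 5.5 says: "We will be available by phone or email to answer questions that may arise during participation". Section 7.3 implies at least three contact attempts for people who consent but do not complete, and does not mention asking about events. Section 2.3.1 names psychological stress from imagining a cancer diagnosis as a risk. For distress, section 2.3.3 says: "They will be reminded to contact their provider if they experience emotional distress".

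**The concern.** The plan commits to counting adverse events but does not describe how one comes to be known. Staff do not observe the session, the survey does not ask, and nobody is scheduled to call a completer afterwards. For the psychological harm that the protocol itself names, the stated advice leads to the participant's own provider, who is given no reporting role.

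Two uses of the count are affected. The DMC's recommendations and the grounds for suspension in section 10.1.2, which include unacceptable risk, rely on it while the study runs. Later, a published statement that no adverse events occurred would be read as evidence of safety, although participants had not been asked. Events that were never collected cannot be recovered at analysis.

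**Working it through.** **Tracing the route of an event.**

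1. *During the session.* The participant is alone at home (section 4.1). Staff can be reached by phone or email for questions (section 5.5), so the participant must start the contact.
2. *In the survey.* None of the measures in section 8.1 asks about adverse events. STAI-6 and cancer fear are taken before and after the video, but no score leads to an event record.
3. *After the session, completers.* No contact is planned.
4. *After the session, non-completers.* Section 7.3 implies contact attempts, with no enquiry about events described.
5. *In the DMC report.* Section 10.1.6 lists study objectives, accrual, demographic balance and the adverse-event summary. The anxiety and fear scores are not listed, and no interim analysis is planned (sections 9.4.6 and 10.1.6).

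The count therefore consists of what participants volunteer, plus whatever staff happen to learn.

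**Inputs for the size.** N = 118 (section 5.5; 2 × 59 in section 9.2). The plan states no adverse-event figure to reproduce. Two quantities are assumptions: p, the true proportion of participants with a reportable event, and c, the share of those events that reaches staff. Participants are taken as independent, with the same p and c.

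**Formulas.** Expected reports = 118 × p × c. P(zero reports) = (1 − p × c)^118. With zero reports, the one-sided 95% upper limit for p × c is 1 − 0.05^(1/118) = 2.5%. Dividing by c gives the limit for p.

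**Results at p = 5%.**

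| c | p × c | Expected reports | P(zero reports) | Upper limit for p after zero reports |
|---|---|---|---|---|
| 10% | 0.005 | 0.59 | 0.995^118 = 55% | 2.5% / 0.10 = 25% |
| 20% | 0.010 | 1.18 | 0.990^118 = 31% | 2.5% / 0.20 = 12.5% |
| 25% | 0.0125 | 1.48 | 0.9875^118 = 23% | 2.5% / 0.25 = 10% |
| 50% | 0.025 | 2.95 | 0.975^118 = 5% | 2.5% / 0.50 = 5% |
| 100% | 0.050 | 5.90 | 0.950^118 = 0.2% | 2.5% |

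The last column does not depend on the assumed p. A zero count would normally be read as a rate below 2.5%. That reading is valid only if essentially every event reaches staff. If a quarter do, the same zero is compatible with rates up to 10%.

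**A higher rate.** At p = 10% and c = 20%, P(zero reports) = 0.98^118 = 9%. A frequent harm would probably produce some reports even under poor capture.

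**The case against.** The strongest reply is that the named harm is already measured. STAI-6 and cancer fear are collected before and after the video and compared by arm, so a shift in distress at group level will show in the results. This stands, and it is the main reason the point is minor. It does not close the gap. The scores are not tied to event reporting or listed in the DMC reports. Participants may also skip questions or stop (section 2.3.3), so the most distressed may have no post-video score.

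Second, routes to staff do exist: phone and email availability, contact attempts for non-completers, a general statement in section 2.3.3 that staff will watch for harms, and the PI's duty to identify events. A reader might infer that participants have no contact with staff, or that no event can reach the DMC. The documents do not support that. What they lack is a contact or item that asks about adverse events, and any planned follow-up of completers.

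Third, a reader might infer that the count will be near zero whatever the true rate. That holds only if almost nothing reaches staff, which no passage states. The 9% result above shows how it fails at a higher rate.

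Fourth, sections 2.3.3 and 10.1.6 might be read as contradicting each other on where distress is to be reported. They do not: section 10.1.6 gives participants no instruction on that.

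Finally, the participant information page and the survey screens are not in the documents and may contain a reporting instruction. If so, the protocol text needs only to say so.

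**Conclusion.** The point holds as a minor, inexpensive improvement. The plan promises a count of adverse events and schedules their reporting at the session, but describes no step that elicits them, so the count rests on volunteered reports. How uninformative a zero would be depends on the capture share, which is unknown: at a 5% event rate, the chance of zero reports in 118 runs from 55% at 10% capture to 0.2% at full capture. Both the rate and the capture shares are assumptions chosen to show the range, not estimates. The study is minimal risk, section 2.3.1 reports no known adverse outcomes in similar studies, and the primary endpoint and its analysis are unaffected.

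**What to change.** - Add one closing Qualtrics item, placed after all endpoints so that it cannot influence them: whether anything in the study was upsetting, how much, and whether the participant wants the study team to make contact.
- Ask the same question in the section 7.3 contacts with non-completers, since a closing item misses those who leave early.
- State in section 10.1.6 and in the schedule row that these responses plus spontaneous contacts are the source of the event count, tabulated by arm. The statisticians who prepare the DMC reports can do the tabulation, so that study staff remain unaware of assignment.
- State in advance which responses are recorded as adverse events, and keep milder reactions as a separate descriptive tally. Some upset is expected when people imagine a cancer diagnosis, and without a rule the item would inflate the count. Where the line falls is for the sponsor and the IRB.
- Leave the advice to contact a provider unchanged.

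The cost is one survey item, a few sentences of protocol text and a minor IRB amendment. Existing staff would have a few more responses to review and log. Contact requests would have to be linked back to the separately stored participant log.
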